## 1. Introduction

### 1.1 Study Purpose

To evaluate the fusion rate and clinical outcomes at 1 year of 20 patients with DDD who undergo a 1 or 2 level TLIF with Tritanium® PL cage and pedicle screw fixation. The proposed case series will build on the body of clinical and radiological evidence for this implant in TLIF patients. It will also provide pilot data for future studies that will compare the Tritanium ® cage to PEEK.

### 1.2 Background

TLIF addresses a range of painful degenerative pathology including DDD and spondylolisthesis. PEEK cages are the standard of care for use in TLIF, however titanium cages have shown good results compared to PEEK in the literature.

### 1.3 Device

Tritanium ® PL is an intervertebral body fusion device indicated for use with autograft and/or allogenic bone graft comprised of cancellous and/or corticocancellous bone graft when used as an adjunct to fusion in patients with degenerative disc disease (DDD) at one level or two contiguous levels from L2 to S1. The Tritanium ® PL cage is a 3D manufactured titanium cage designed with angled serrations for bidirectional fixation and to maximize surface area for endplate contact with the implant. The cage is also designed to address the potential for subsidence into the endplates.

The Tritanium® PL Cage was cleared for marketing under 510(k) K160955

### 1.4 Study Objectives

- Primary Objective
  - Assess fusion at 1 year post-operatively on CT
- Secondary Objectives

- Assess pain and functional outcomes using VAS and ODI (validated patient reported outcomes)
- Assess hardware placement and fusion with plain radiographs collected at 2 weeks, 6 months and 12 months post-op.
- Monitor adverse events

## 2. Study Hypothesis

The Titanium PL cage will produce satisfactory fusion rates due to its highly porous material designed for bone in-growth and biologic fixation. TLIF fusion rate, adverse events and patient reported outcomes will be qualitatively comparable to PEEK results in the literature.

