## 3. Study Methods

### 3.1 Study Design

Prospective, non-randomized (single arm) single-center study to evaluate the post-operative radiographic and patient outcome variables of the Titanium PL cage compared to literature reported outcomes for traditional PEEK cage for interbody fusion treatment of degenerative disc disease (DDD).

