### 3.3 Primary Study Endpoint

## Fusion status at 1 year

### 4. Study Population

#### 4.1 Sample size

20 patients will be enrolled in the study. Outcomes from this pilot study may be used to design larger controlled trials.

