### 5. Study Objectives/Outcomes

#### 5.1 Primary Study Objective

Evaluate fusion status at 1 year (12 months)

- Radiographic Assessment of Fusion

Radiographic assessments by CT scan and AP/ lateral x-rays at the 12 month visits include overall assessment of fusion. Fusion will be graded by the Principle Investigator taking into account signs such as:

- Bony Bridging
- Radiolucency
- Development of Pseudoarthrosis

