## 10. Statistical Methods

The purpose of this study is to build upon the available data for the Tritanium implant in this on-label population. Descriptive statistics will be used to summarize demographics and baseline and surgical variables.

Change in in VAS and ODI will be determined and the percentage of patients exceeding the MCIC (minimally clinical important change) will be reported for each outcome. The MCIC to be used for each patient reported outcome are derived from Parker, et al, *J Neurosurgery Spine*, 2011.

- VAS – Leg pain- 2.8
- VAS – Back Pain- 2.1
- ODI – 14.9

The fusion rate will be reported and qualitatively compared to TLIF fusion rates in the literature.

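### The hypothesis of satisfactory fusion comparable to PEEK has no benchmark, interval or result that would count against it, and 20 single-arm patients cannot support a comparability conclusion

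*Combined protocol and SAP*

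**What the plan says.** Section 2 (Study Hypothesis) makes two predictions. The first is "The Titanium PL cage will produce satisfactory fusion rates". The second is "TLIF fusion rate, adverse events and patient reported outcomes will be qualitatively comparable to PEEK results in the literature". Section 3.1 sets the same literature comparison into the design, described as a "Prospective, non-randomized (single arm) single-center study".

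For fusion, Section 10 (Statistical Methods) carries this out in one sentence: "The fusion rate will be reported and qualitatively compared to TLIF fusion rates in the literature". It cites a publication but states no rate from it. Its only other commitments are descriptive summaries of demographic, baseline and surgical variables, and the change in VAS and ODI with the percentage of patients exceeding a cut-off on each (2.8 for leg pain, 2.1 for back pain, 14.9 for ODI). Section 4.1 fixes the size: "20 patients will be enrolled in the study", with no calculation behind it.

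Sections 1.1 and 4.1 present the study as a case series giving pilot data for later controlled work.

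**The concern.** The hypothesis uses words that call for a decision, *satisfactory* and *comparable*, and the plan gives no means of making one. It fixes no reference rate, no interval around the observed rate, and no number fused out of 20 that would count as unsatisfactory or not comparable. The secondary patient-reported outcomes have numerical cut-offs; the primary endpoint has none.

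The meaning of *comparable* can therefore be settled after the 12-month CTs have been read. In a sample this small, a literature rate and a materially lower true rate can both fit the same result, so seeing no obvious difference says little. Section 1.1 intends the data to add to the evidence on the implant and to feed later comparisons with PEEK. A comparability statement resting on this plan could be carried into that work with more weight than it can bear.

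**Working it through.** **Inputs.** From the documents: n = 20 (Section 4.1), one arm (Section 3.1), fusion status at 1 year (Section 3.3). Not given, so assumed: a PEEK reference rate R of 80%, 85%, 90% or 95%; all 20 patients evaluable; one fused/not-fused result per patient. The plan has no power or precision figure to reproduce.

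**Step 1: precision.** For x fused out of n, the exact (Clopper-Pearson) 95% limits are
- lower = the 2.5% quantile of Beta(x, n − x + 1)
- upper = the 97.5% quantile of Beta(x + 1, n − x)

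| Fused | Observed rate | Exact 95% interval |
|---|---|---|
| 18/20 | 90% | 68.3% to 98.8% |
| 17/20 | 85% | 62.1% to 96.8% |
| 15/20 | 75% | 50.9% to 91.3% |

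An observed 90% does not exclude a true rate of 70%. An observed 75% does not exclude a true rate of 90%.

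**Step 2: what *comparable* could mean.** The plan does not say, so four readings were tried. Each sets a smallest number fused, r, at which the result would be called comparable:
- strict: observed rate at or above R
- observed rate no more than 5 points below R
- observed rate no more than 10 points below R
- lenient: the exact 95% interval does not lie wholly below R

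For a cage whose true rate is R − 15 points, the chance of being called comparable is P(X ≥ r), with X ~ Binomial(20, R − 0.15). Each cell gives r, then that chance.

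| Reading | R = 80% | R = 85% | R = 90% | R = 95% |
|---|---|---|---|---|
| At or above R | 16; 11.8% | 17; 10.7% | 18; 9.1% | 19; 6.9% |
| Within 5 points | 15; 24.5% | 16; 23.8% | 17; 22.5% | 18; 20.6% |
| Within 10 points | 14; 41.7% | 15; 41.6% | 16; 41.5% | 17; 41.1% |
| Interval not wholly below R | 12; 76.2% | 14; 60.8% | 15; 61.7% | 17; 41.1% |

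The full range is 6.9% to 76.2%. At R = 90% alone it is 9.1% to 61.7%.

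**Step 3: a cage 10 points worse.** The same calculation with true rate R − 0.10 gives 18% to 24% under the strict reading and 65% to 89% under the lenient one.

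**Step 4: the strict reading has its own cost.** A cage truly equal to the reference passes it with probability 63.0%, 64.8%, 67.7% and 73.6% at the four values of R. It would fail 26% to 37% of the time.

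**The case against.** The strongest reply is that nothing in the plan says comparability will be concluded. Section 2 states an expectation. Section 10 says the rate will be reported and compared qualitatively, and it plans no test, p-value or equivalence claim. The stated objectives are to assess fusion (Section 1.4) and to evaluate fusion status (Section 5.1), which is already close to estimation. A 20-patient pilot need not carry a non-inferiority margin.

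Much of this stands. The absence of a formal test is not an error in a descriptive pilot. A reader might infer that the plan declares comparability by default whenever no difference is seen; no section says so. A reader might also infer that no result could ever refute the hypothesis. The documents support only that no such result is specified in advance; a very low fusion rate would presumably be recognised as poor.

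A third tempting inference is that a clearly worse cage would *often* be called comparable. That holds under the two more lenient readings, but the plan adopts neither the 10-point tolerance nor the interval they use. Under the strict reading a cage 15 points worse passes only 7% to 12% of the time.

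The pilot status does not remove the point, however. A descriptive study of this size supports an estimate, and that is why a hypothesis of satisfactory and comparable fusion does not fit it. The 7% to 76% spread measures how much the plan leaves open.

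**Conclusion.** The point holds as a mismatch between the hypothesis and what the analysis can support. *Satisfactory* and *comparable* are undefined, no interval is planned for the primary endpoint, and the benchmark is not stated as a number. A comparability conclusion drawn from the plan as written would not be sound.

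With 20 evaluable patients, the exact 95% interval is about 30 points wide at 18/20 (98.8 − 68.3 = 30.5) and about 40 points wide at 15/20 (91.3 − 50.9 = 40.4). The chance that a cage 15 points worse is called comparable is about 7% to 76%. That range rests on an assumed reference of 80% to 95% and on the four readings tried; no single value within it can be taken from the documents. The intervals need only n = 20 with one result per patient.

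**What to change.** **Section 2.** Replace the prediction of satisfactory and comparable results with an aim: to estimate the 12-month fusion rate, and to describe adverse events and patient-reported outcomes, in order to inform a later controlled comparison with PEEK.

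**Section 10.** Report the fusion rate with an exact (Clopper-Pearson) 95% interval beside the literature rate. State that the absence of an apparent difference from the literature will not be reported as comparability.

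A formal non-inferiority rule is not needed. Its reference and margin would have no source in the documents, and it would cover fusion only. With an illustrative 15-point margin and a one-sided 95% lower limit, it would require 17, 18, 19 or 20 of 20 fused at references of 80%, 85%, 90% and 95%. A cage equal to PEEK would then pass only 36% to 41% of the time.

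**Cost.** A few sentences of wording and one interval calculation, with no added patients, visits or imaging. The downside is a weaker claim: the report gives an estimate with wide limits and does not state that the cage matches PEEK.

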## 3. Study Methods

### 3.1 Study Design

Prospective, non-randomized (single arm) single-center study to evaluate the post-operative radiographic and patient outcome variables of the Titanium PL cage compared to literature reported outcomes for traditional PEEK cage for interbody fusion treatment of degenerative disc disease (DDD).

### 3.2 Treatment Group

20 patients requiring an open 1 or 2 level TLIF will make up the study population. Eligible patients will have lumbar (L2-S1) degenerative disc disease (may have up to grade 1 spondylolisthesis), and/ or degenerative scoliosis. DDD is defined as back pain of discogenic origin with degeneration of the disc confirmed by history and radiographic studies. The DDD patients may also have up to Grade I spondylolisthesis at the involved level(s). These patients should be skeletally mature and have six months of non-operative therapy.

### 3.3 Primary Study Endpoint

## Fusion status at 1 year

### 4. Study Population

#### 4.1 Sample size

20 patients will be enrolled in the study. Outcomes from this pilot study may be used to design larger controlled trials.

#### 4.2 Inclusion and Exclusion Criteria

Patients must meet all of the inclusion criteria and none of the exclusion criteria in order to be eligible to enter the study.

- Inclusion Criteria
  - Subject has one or more of the following diagnoses:
    - Degenerative disc disease (DDD) at one level or two contiguous levels from L2 to S1.
    - DDD may also include up to Grade I spondylolisthesis at the involved level(s).
    - Note: DDD is defined as back pain of discogenic origin with degeneration of the disc confirmed by history and radiographic studies.
    - Degenerative scoliosis for which the Titanium PL cage will be used as an adjunct to fusion.
    - Skeletally mature and  $\geq 18$  years old at time of enrollment
    - Completed at least 6 months of non-operative therapy prior to surgery
    - Willing and able to sign a study specific consent and comply with the requirements of the protocol including follow up visits and imaging.

- Exclusion Criteria
  - >2 levels requiring surgical intervention
  - Non-degenerative pathology including tumor, trauma, post-laminectomy kyphosis
  - Psudeoarthrosis at the index level
  - Previous fusion at the levels to be treated or at adjacent level
  - Any abnormality present which affects the normal process of bone remodeling including, but not limited to, severe osteoporosis involving the spine, bone absorption, osteopenia, primary or metastatic tumors involving the spine, active infection at the site or certain metabolic disorders affecting osteogenesis.
  - History of osteoporotic fracture
  - History of an endocrine or metabolic disorder known to affect bone and mineral metabolism
  - Inadequate tissue coverage over the operative site or taking medications that may interfere with bony/soft tissue healing including chronic steroid use
  - Known allergy to titanium or cobalt chrome or may be sensitive to materials
  - Rheumatoid arthritis or other autoimmune disease or a systemic disorder such as HIV, active hepatitis B or C or fibromyalgia
  - Lumbar kyphosis- lumbar lordosis < 20°

- Degenerative scoliosis  $>20^\circ$  OR any other pathology scoliosis (idiopathic, congenital, posttraumatic, iatrogenic)
- Active systemic infection or infection at the operative site
- Marked local inflammation
- Any open wounds
- Pregnant, or intends to become pregnant during the study
- Current smokers
- Subject is class 3 obese (BMI  $>40$ ) or overweight and can produce loads on the spinal system which can lead to failure of the fixation of the device or to failure of the device itself
- Any mental or neuromuscular disorder which would create an unacceptable risk of fixation failure or complications in postoperative care
- Any neuromuscular deficit which places an unsafe load level on the device during the healing period
- Any other medical or surgical condition which would preclude the potential benefit of spinal implant surgery, such as the presence of tumors, congenital abnormalities, elevation of sedimentation rate unexplained by other diseases, elevation of white blood cell count (WBC), or marked left shift in the WBC differential count.
- Any condition of senility, mental illness, or substance abuse.
- Involved in current spinal litigation that may interfere or influence patient self-assessment of function and pain

- Physical or mental condition that may interfere or influence patient self-assessment of function and pain.
- Incarcerated at the time of study enrollment

#### 4.3 Study Duration

Study subjects will be expected to participate in this study for 12 months following surgery, with follow-up evaluations at initial post-op (2 weeks), 3 months, 6 months, and 12 months.

### 5. Study Objectives/Outcomes

#### 5.1 Primary Study Objective

Evaluate fusion status at 1 year (12 months)

- Radiographic Assessment of Fusion

Radiographic assessments by CT scan and AP/ lateral x-rays at the 12 month visits include overall assessment of fusion. Fusion will be graded by the Principle Investigator taking into account signs such as:

- Bony Bridging
- Radiolucency
- Development of Pseudoarthrosis

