# 7. Hospitalization/Surgical Technique/Discharge

Subjects will be admitted to the hospital according to the Principle Investigator's standard for an instrumented posterolateral fusion in conjunction with a TLIF surgery. Prophylactic antibiotics, preoperative planning, patient positioning and anesthesia will be carried out in accordance with the institution's and Investigator's standard of care.

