## 7.1 Surgical Approach

The surgeon performs a midline incision and standard posterior exposure to decorticate the transverse processes bilaterally to accommodate graft for the posterior fusion. The spinous processes and interspinous ligaments can usually be left intact, which minimizes epidural scarring and provides a larger surface area for the posterior fusion.

After exposure, pedicle screws are placed bilaterally. Fluoroscopy or other strategies may be used to aid in proper screw positioning. Distraction may then be performed using the surgeon's preferred method to open the posterior portion of the disc space, if needed.

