## 7.2 Transforaminal Lumbar Interbody Fusion (TLIF)

For the TLIF procedure, access to the disc space is gained via a triangular working window. The window is formed by the traversing nerve root and thecal sac on the medial side, the exiting nerve root from the proximal vertebral level on the lateral side, and the superior aspect of the pedicle of the distal vertebra forms the base of the triangle. The surgeon performs a laminotomy, laminectomy and/or facetectomy (partial or total) along with removal of the ligamentum flavum to provide access to the disc space. Care should be taken to preserve the facets as much as possible and remove only enough bone as needed to provide access for introduction of the interbody spacer and to decompress and mobilize the nerve root as necessary. If decompression of the contralateral side of the spinal canal is required, the TLIF procedure can be modified to include a central laminectomy.

After exposure of the posterior aspect of the disc, an incision is made in the annulus through which the discectomy and endplate preparation are performed. Endplate preparation consists of removal of the cartilaginous endplate down to bleeding bone. The Titanium PL interbody cage is then introduced.

Once the interbody implant is in place and bone graft added to the disc space, distraction is released and compression is applied to the pedicle screw to load the anterior implant and restore lordosis to the spine.

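### The primary fusion endpoint does not say which of two graft sites must fuse, so a patient fused only posterolaterally could count towards a rate that the hypothesis credits to the cage

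*Combined protocol and SAP*

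**What the plan says.** The primary objective in Section 1.4 is "Assess fusion at 1 year post-operatively on CT", and Section 3.3 gives the primary endpoint as "Fusion status at 1 year". Section 5.1 adds how it is to be read: "Radiographic assessments by CT scan and AP/ lateral x-rays at the 12 month visits include overall assessment of fusion". It continues: "Fusion will be graded by the Principle Investigator taking into account signs such as" bony bridging, radiolucency and pseudoarthrosis. Section 10 reports the resulting rate and compares it qualitatively with published TLIF rates.

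Section 7 describes the operation as "an instrumented posterolateral fusion in conjunction with a TLIF surgery". In Section 7.1 the exposure is made "to decorticate the transverse processes bilaterally to accommodate graft for the posterior fusion". Section 7.2 covers the disc space: "Once the interbody implant is in place and bone graft added to the disc space", the construct is compressed. The technique as described therefore has two graft beds, and no option to omit the posterior one is stated.

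The hypothesis in Section 2 is about the implant: "The Titanium PL cage will produce satisfactory fusion rates due to its highly porous material designed for bone in-growth and biologic fixation".

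**The concern.** The cage sits in the disc space, and its porous surface can promote bone growth only there. The posterolateral graft lies on the transverse processes and may fuse or fail for its own reasons. One overall grade can merge the two.

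If the investigator accepts bridging at the transverse processes as fusion, a patient with an unfused disc space counts as a success for the cage. A reader of the final report could not tell whether that had happened, because only one grade is planned.

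Fusion at 1 year is the study's main product. Its only planned use in Section 10 is a comparison with published rates, and Section 1.1 also offers the study as pilot data for later comparisons of this cage with PEEK. Both uses need to know which site the rate describes.

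**Working it through.** The plan gives no expected fusion rate, power calculation or site-specific rate, so there is no figure of its own to reproduce. The check is mainly a reading of each section that bears on the site.

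**Step 1. Is there more than one graft site?** Yes. Section 7.1 prepares the transverse processes on both sides for graft, and Section 7.2 adds graft to the disc space around the cage. These sections describe general technique. That both beds are grafted at every treated level is the natural reading, but it is not stated level by level.

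**Step 2. Does the endpoint name a site?**
- Section 1.4: fusion on CT; no site.
- Section 3.3: fusion status; no site.
- Section 5.1: overall assessment on CT and plain films, from an open list of signs; no sign is tied to a site and posterolateral bridging is not excluded.
- Section 10: the fusion rate; no site and no rule for the numerator.

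**Step 3. Does other wording settle it?** Section 2 speaks of the fusion rate for TLIF, Section 3.1 of a cage for interbody fusion, and Section 10 of TLIF rates in the literature. Section 7 treats the posterolateral fusion and the TLIF as two procedures done together. All of this leans towards the disc space. None of it stands in the endpoint or the grading rule.

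**Step 4. What would a reclassified patient do to the rate?** Let n be the number of evaluable patients, I the number with interbody fusion, and k the number whose only fusion is posterolateral but who are graded as fused.
- Interbody rate = I/n
- Reported rate = (I + k)/n
- Difference = k/n

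With n = 20 (Section 4.1) and k = 1, the difference is 1/20 = 5 percentage points. With fewer evaluable patients each one weighs more; for an assumed n = 18, 1/18 = 5.6 points. The documents give neither I nor k, and k may be 0.

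**Step 5. Scale against sampling error.** As an illustration with assumed counts, take I = 16 and k = 1:
- 16/20 = 80%, exact (Clopper-Pearson) 95% CI 56.3% to 94.3%
- 17/20 = 85%, exact 95% CI 62.1% to 96.8%

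One patient's shift is small beside either interval. The issue is therefore what the estimate means more than how precise it is.

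**Step 6. Size of the remedy.** Twenty patients with one or two treated levels give 20 × 1 = 20 to 20 × 2 = 40 levels to grade.

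**The case against.** The strongest reply is that the protocol's own vocabulary points to the disc space. It calls the transverse-process graft the posterior fusion, describes TLIF as the disc-space procedure, and frames both the hypothesis and the literature comparison in terms of TLIF. On that view a sensible investigator would grade the interbody space. The word *overall* in Section 5.1 most naturally means a global judgement across imaging methods and signs, not across anatomical sites.

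Much of this stands. The text leans towards interbody, and *overall* alone proves nothing about site. But a lean drawn from the hypothesis and design sections is not an endpoint definition. The section that instructs the grader leaves posterolateral bone eligible.

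A second reply is that this is a descriptive pilot with no test, threshold or success criterion, and that its interval will be wide whatever the definition. That also stands: no error rate or formal decision is affected. A descriptive study still has to say what its main estimate measures.

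A third reply is that site is only one gap, since Section 5.1 also lacks a grading scale. That is fair, and naming the site will not by itself make the grading reproducible.

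Two stronger readings are tempting. A reader might infer that the endpoint could require fusion at both sites, so that a fused disc space with a failed posterolateral bed would be marked as not fused. Nothing in the documents suggests this. A reader might also infer that the reported rate will be inflated. The documents do not show that any patient will be fused only posterolaterally, or that the investigator would count such a patient.

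**Conclusion.** The concern holds as a gap in the definition of the primary endpoint. Two graft beds are planned, one undivided grade is recorded, and the hypothesis attributes the result to the implant in one of them. As written, a patient bridged only posterolaterally can be counted as fused.

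The supported size is 5 percentage points per reclassified patient, assuming all 20 are evaluable. How many patients would be affected, if any, cannot be determined from the documents. The conclusion rests on the surgical technique being carried out as described and on no unstated grading convention being in force.

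This should be changed, although the study can run without it. Separate grading is a better method than one overall grade, and it lets the study address its own hypothesis. It does not remove the limits of a single-arm design or separate the cage's contribution from that of the pedicle screws.

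**What to change.** - **Sections 3.3 and 5.1:** define the primary endpoint as interbody fusion, meaning bridging bone through or around the cage, at each treated disc space on the 12-month CT.
- **Section 5.1:** grade the posterolateral bed separately on the same CT. Keep overall fusion as a secondary result, with a sentence saying how it is derived.
- **Section 10:** report interbody and posterolateral fusion counts per treated level, and the per-patient interbody rate with an exact 95% CI.

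The per-patient rate also needs a rule for a two-level patient with one fused and one unfused disc space. That is a separate point and is not decided here.

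**Cost:** the CT is already planned, so there are no extra patients, visits or scans. The work is one more grading line per treated level (20 to 40 in all) and a few sentences of text. The downside is that the primary rate may match less well with literature series that report overall fusion; keeping overall fusion as a secondary result limits that loss.

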## 6.2 Follow Up Visits

Patients will return to clinic to complete subject questionnaires (ODI and VAS) at 2 weeks, 3 months, 6 months, and 12 months postoperatively. Plain radiographs (AP and Lateral views) will be obtained at 2 weeks, 6 months and 12 months. A CT scan will also be obtained at 12 months.

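### The primary endpoint is one investigator's grade from an open list of signs, with no fused/not-fused rule and no masking; a masked read by the same reader against pre-set criteria would be a cheap improvement

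*Combined protocol and SAP*

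**What the plan says.** All references are to the combined protocol and SAP.

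- **Endpoint.** Section 3.3 names one primary endpoint, "Fusion status at 1 year", and attaches no definition.
- **Images.** Section 1.4 points to CT: "Assess fusion at 1 year post-operatively on CT". Section 5.1 adds plain films: "Radiographic assessments by CT scan and AP/ lateral x-rays at the 12 month visits include overall assessment of fusion". No rule covers disagreement between the two.
- **Reader and criterion.** Section 5.1: "Fusion will be graded by the Principle Investigator taking into account signs such as" bony bridging, radiolucency and the development of pseudoarthrosis. There is no scale, threshold, required combination of signs, or category for an uncertain scan.
- **Unit.** Section 3.2 allows one or two treated levels per patient. The plan does not say whether the fusion rate is per patient or per level.
- **Clinical data at the same visit.** Under section 6.2 patients "complete subject questionnaires (ODI and VAS) at 2 weeks, 3 months, 6 months, and 12 months postoperatively", and the CT is also obtained at 12 months.
- **The reader's other roles.** Pre-operative imaging is judged against the investigator's surgical planning needs (6.1), admission follows the investigator's standard (7), and return to activity is at the investigator's discretion (7.3).
- **Masking.** No section mentions masking, de-identification, a second reader or a repeat read.
- **Use of the result.** Section 10: "The fusion rate will be reported and qualitatively compared to TLIF fusion rates in the literature". Section 2 expects satisfactory fusion rates.

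**The concern.** This is a "Prospective, non-randomized (single arm) single-center study" with no control group, no test and no success threshold. Its main product is a single proportion, to be set beside published rates and used as pilot data for later comparisons with PEEK (1.1). The meaning of that proportion depends entirely on how a scan comes to be called fused.

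Two things are missing. First, without a stated rule the standard can drift from patient to patient, and a reader of the report cannot tell whether fused means the same here as in the comparison studies. Pseudoarthrosis adds little as a criterion, since it is close to a restatement of non-fusion. Second, the reader is involved in the patients' care and nothing separates the grade from who the patient is or how the patient is doing. An equivocal scan in a patient who is doing well could be called fused, and one in a patient still in pain could be called not fused. A lenient reading of equivocal scans would favour the hypothesis in section 2.

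**Working it through.** The plan states no expected fusion rate, precision target, alpha or power, so there is no figure of its own to reproduce. Section 4.1 gives the number alone: "20 patients will be enrolled in the study. Outcomes from this pilot study may be used to design larger controlled trials". What follows is illustration, with assumptions marked.

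**1. Weight of one grade.** N = 20 (section 4.1). If the rate is per patient, one changed grade moves it by 1/20 = 5 percentage points. If it is per level, the denominator lies between 20 (all one-level) and 40 (all two-level), so one changed level moves it by between 1/20 = 5 and 1/40 = 2.5 points. The plan does not say which applies.

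**2. Effect of equivocal scans.** Assume that two patients have equivocal scans and 16 of the other 18 are clearly fused. Exact (Clopper-Pearson) 95% intervals:

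- both equivocal scans counted as not fused: 16/20 = 80% (56.3 to 94.3)
- both counted as fused: 18/20 = 90% (68.3 to 98.8)

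The difference is 2 × 5 = 10 points; four equivocal scans would give 4 × 5 = 20 points. The number of equivocal scans is assumed. This shows the effect of the counting rule. It does not measure the gain from masking.

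**3. Effect of reader error in general.** Let p be the true fusion rate, Se the chance that a fused patient is graded fused, and Sp the chance that a non-fused patient is graded not fused. Then

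expected observed rate = p × Se + (1 − p) × (1 − Sp).

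Example: p = 0.80, Se = 1, Sp = 0.8 gives 0.80 + 0.20 × 0.2 = 0.84, a bias of +4 points. All values of p, Se and Sp are assumed.

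| True rate | Se | Sp = 0.8 | Sp = 0.6 | Sp = 0.4 |
|---|---|---|---|---|
| 70% | 1 | 76% (+6) | 82% (+12) | 88% (+18) |
| 80% | 1 | 84% (+4) | 88% (+8) | 92% (+12) |
| 90% | 1 | 92% (+2) | 94% (+4) | 96% (+6) |
| 70% | 0.95 | 72.5% (+2.5) | 78.5% (+8.5) | 84.5% (+14.5) |
| 80% | 0.95 | 80% (0) | 84% (+4) | 88% (+8) |
| 90% | 0.95 | 87.5% (−2.5) | 89.5% (−0.5) | 91.5% (+1.5) |

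A purely lenient reader (Se = 1) inflates the rate. Once a few fused patients are missed (Se = 0.95), the net bias runs from −2.5 to +14.5 points and its sign is no longer fixed. The documents give no reader-accuracy data, so no row can be chosen as the true one.

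**The case against.** The strongest reply is that this is a 20-patient descriptive pilot. No type I error, power or success criterion is at risk, and a 10-point shift lies well inside the sampling error shown above. The endpoint is also not unstructured: it rests on imaging, includes CT and names three signs. All of that stands, and it limits how serious the point is. It does not supply a fusion rule, and with no control arm or test nothing else in the design protects the reported rate.

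Four stronger readings are tempting, and the documents do not support them.

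- *That the investigator will grade with the ODI and VAS in view.* The plan says that patients complete the questionnaires. It does not say that the reader sees or uses them. What is shown is a missing safeguard.
- *That the error must run in the favourable direction.* Knowledge of symptoms can push a grade either way, and the calculation gives both signs. Section 2 states a favourable expectation, but that does not establish how the reader behaves.
- *That the harm could never be repaired.* Section 8.3 lists the 12-month CT as study data, so if the images are kept a masked read could still be done late. Criteria chosen after grades are known would carry less weight, which is a reason to set them early.
- *That the move from 80% to 90% is what masking would save.* It is the effect of an assumed number of equivocal scans.

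Masking the same reader also has limits. Every scan shows the study cage, so expectation about the device remains, and at one centre with 20 patients the reader may recall cases, particularly if the same person did the clinical read. It would reduce the influence of patient identity and clinical outcome, but would not remove it or measure agreement between readers.

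**Conclusion.** The point holds as a gap in the definition and safeguarding of the primary endpoint, and it should be corrected. One reader decides fusion from an open list, with no rule for fused, for indeterminate scans, for two-level patients or for discordant CT and plain films, and with no masking. What is at stake is the credibility of the fusion rate and of its comparison with the literature. Any bias has unknown size and direction. The only firm figure is 5 percentage points per changed patient grade, given 20 patients and a per-patient rate; the larger shifts depend on assumed numbers of equivocal scans or assumed reader accuracy. The case for acting rests on the low cost of a better procedure, not on demonstrated bias.

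**What to change.** Add to section 5.1:

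- **Masked read.** After the last 12-month visit, existing study staff de-identify the 12-month CTs and AP/lateral films. The investigator grades them in random order without ODI, VAS or adverse-event data. If CT alone is to decide, as section 1.4 suggests, say so and mask the CTs only. The routine clinical read stays separate and is not the study grade.
- **Criteria and unit.** The signs required for fused are written down before the first 12-month scan is read. Each treated level is scored fused, not fused or indeterminate on a one-page form. The primary rate is per patient, with a two-level patient fused only if both levels are fused; the per-level rate is also reported.
- **Indeterminate scans.** Report their number, and show the rate with them counted as not fused and as fused. Name the former as primary in advance.

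Cost: a short protocol paragraph, the form, and one reading session for about 20 patients by the existing reader. The study grade waits until the last 12-month visit, the reported rate may be slightly lower, and masking is partial for the reasons given above.
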